#### **10.4.9. Cardiovascular Risk**

##### **10.4.9.1. Adjudicated Cardiovascular Events**

Adjudicated cardiovascular events, including Major Adverse Cardiovascular Events (MACE) (defined as death, myocardial infarction, and stroke) and other related events including hospitalization for unstable angina, revascularization procedures, hospitalization for congestive heart failure, transient ischemic attack, and additional events related to adverse cardiovascular outcomes, will be included in the CEC Charter for adjudication. The adjudication of these events will be handled separately from the adjudication of events for assessment of the primary clinical composite outcome endpoint in this study.

Summaries of adjudicated cardiovascular events including MACE will include the overall summary of cardiovascular TEAEs, incidence of TEAEs, incidence of serious TEAEs, annualized adjudicated CV event rate, and a time-to-event analysis as described below. All summaries of incidence will include the associated exact binomial 95% confidence interval (CI). Summaries will be carried out for the Safety Population and ITT Population.

The time-to-event endpoints include:

- Time from randomization to the first confirmed occurrence of cardiovascular death, nonfatal myocardial infarction, nonfatal stroke
- Time from randomization to the confirmed occurrence of cardiovascular death (including fatal myocardial infarction, fatal stroke)
- Time from randomization to the first confirmed occurrence of myocardial infarction (nonfatal or fatal)

- Time from randomization to the first confirmed occurrence of stroke (nonfatal or fatal)
- Time from randomization to the confirmed occurrence of death from any cause
- Time from randomization to the first confirmed occurrence of unstable angina requiring hospitalization (nonfatal or fatal)
- Time from randomization to the first occurrence of coronary revascularization procedure
- Time from randomization to the first occurrence of hospitalization for congestive heart failure
- Time from randomization to the first occurrence of transient ischemic attack
- Time from randomization to the first occurrence of hospitalization for clinically significant arrhythmias
- Time from randomization to the first occurrence of hospitalization for peripheral revascularization procedures

In addition, subjects with any adjudicated cardiovascular event will be presented by the following lipid subgroups:

- Total Cholesterol (TCHOL): Mean and median TCHOL values by visit after first dose of investigational product.
- HDL: Mean and median HDL values by visit values after first dose of investigational product
- LDL: Mean and median LDL values by visit after first dose of investigational product
- LDL/HDL: Mean and median LDL/HDL values by visit after first dose of investigational product
- Apolipoprotein B: Mean and Median apolipoprotein B values by visit after first dose of investigation product

Subgroup analysis by prior CV disease, by CV risk factors (eg, FRS), by baseline type 2 diabetes mellitus (T2DM) status will be performed.

Additional analyses for all adjudicated CV events will include:

- EAIR of CV cases adjudicated for ALL cases of CV by severity and treatment arms
- EAIR of CV cases adjudicated as  $\geq$  possible causality and severity by treatment arms

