16.9.3. Cardiovascular Event Adjudication

Adjudicated cardiovascular events include core MACE (cardiovascular death, nonfatal myocardial infarction, and nonfatal stroke) and expanded MACE (unstable angina requiring hospitalization, transient ischemic attack, peripheral or coronary revascularization procedures, hospitalization for congestive heart failure and arrhythmias). Any hospitalization (≥ 24 hours) where a cause has not been identified by the Investigator will be treated as a cardiovascular event and sent for adjudication. Other events potentially related to adverse cardiovascular outcomes are defined in [Appendix E](#) and will be included in the Cardiovascular Adjudication Committee (CAC) Charter for adjudication. The adjudication of these events will be handled separately from the adjudication of events for assessment of the primary endpoint in this study (See

Section 16.11). Undetermined cause of death will be classified as a cardiovascular death by the CAC.

There will be no formal hypothesis testing of MACE at the Month 18 Interim Analysis. The EOS assessment of MACE will include all MACE events occurred from the start of the study.

Summaries of adjudicated cardiovascular events will include the incidence of TEAEs, the incidence of serious TEAEs, and a time-to-event analysis as described below. All summaries of incidence will include the associated exact binomial 95% CI.

The time-to-event endpoints include:

- Time from randomization to the first confirmed occurrence of cardiovascular death, nonfatal myocardial infarction, nonfatal stroke, or nonfatal unstable angina requiring hospitalization
- Time from randomization to the confirmed occurrence of cardiovascular death (including fatal myocardial infarction, fatal stroke)
- Time from randomization to the first confirmed occurrence of myocardial infarction (nonfatal or fatal)
- Time from randomization to the first confirmed occurrence of stroke (nonfatal or fatal)
- Time from randomization to the confirmed occurrence of death from any cause
- Time from randomization to the first confirmed occurrence of unstable angina requiring hospitalization (nonfatal or fatal)
- Time from randomization to the first occurrence of coronary revascularization procedure
- Time from randomization to the first occurrence of hospitalization for congestive heart failure
- Time from randomization to the first occurrence of transient ischemic attack
- Time from randomization to the first occurrence of arrhythmia

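### The SAP's definition of MACE counts death without the cardiovascular qualifier, in conflict with the protocol and with the SAP's own endpoint list, and the protocol's four-component first-event endpoint is missing

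*SAP*

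**What the plan says.** SAP Section 10.4.9.1 is the only place where the SAP says what MACE contains: "Major Adverse Cardiovascular Events (MACE) (defined as death, myocardial infarction, and stroke". The sentence goes on to name other cardiovascular events and ends by referring them to the adjudication charter. The next paragraph specifies the output, which extends to a yearly rate and a time-to-event analysis: "Summaries of adjudicated cardiovascular events including MACE will include the overall summary of cardiovascular TEAEs, incidence of TEAEs, incidence of serious TEAEs, annualized adjudicated CV".

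Protocol Section 16.9.3 differs: "Adjudicated cardiovascular events include core MACE (cardiovascular death, nonfatal myocardial infarction, and nonfatal stroke". The Synopsis and Section 12 agree with it. Section 16.9.3 also classifies deaths of undetermined cause as cardiovascular.

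The first time-to-event endpoint differs too. The protocol has four components: "Time from randomization to the first confirmed occurrence of cardiovascular death, nonfatal myocardial infarction, nonfatal stroke, or nonfatal unstable angina requiring hospitalization". The SAP has three: "Time from randomization to the first confirmed occurrence of cardiovascular death, nonfatal myocardial infarction, nonfatal stroke". The SAP also lists two separate endpoints that matter here: "Time from randomization to the first confirmed occurrence of unstable angina requiring hospitalization (nonfatal or fatal" and "Time from randomization to the confirmed occurrence of death from any cause".

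**The concern.** Read literally, the SAP definition puts every death into MACE, including deaths from liver disease, cancer or COVID-19. Those deaths will be in the cardiovascular committee's data, because SAP Section 6.4.3 sends all deaths to that committee. A programmer who follows the text could therefore count them. The same section would then produce two different sets of MACE events, one for the incidence and rate tables and another for the first time-to-event endpoint.

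This affects a stated objective. Protocol Section 5.5 reports that OCA raises LDL cholesterol and says that longer treatment and more subjects are needed to assess cardiovascular risk. SAP Section 2.1.2.4 lists incidence, exposure-adjusted incidence and time to adjudicated cardiovascular events among the End of Study safety objectives. An incidence table that mixes in other deaths answers a different question, and all-cause death already has its own endpoint.

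**Working it through.** **Step 1: compare the texts.**

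| Source | Death component | Unstable angina in the composite |
|---|---|---|
| Protocol 16.9.3, core MACE | cardiovascular | no |
| Protocol 16.9.3, first time-to-event endpoint | cardiovascular | yes |
| SAP 10.4.9.1, MACE definition | unqualified | no |
| SAP 10.4.9.1, first time-to-event endpoint | cardiovascular | no |

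The third row disagrees with the other three on death. The SAP definition also omits the word nonfatal for infarction and stroke. That matters little, because a fatal infarction or stroke is already a cardiovascular death. The second row has no counterpart in the SAP.

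**Step 2: find which outputs are exposed.** The first time-to-event endpoint spells out its own components, so it does not depend on the definition. The incidence and annualized-rate summaries refer to MACE by name and do depend on it.

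**Step 3: illustrate the size.** The plan gives no MACE rate, event target or power, so there is no figure to reproduce. All counts below are assumed. Each added death is taken to be in a subject with no earlier infarction or stroke, and the two arms are taken as equal in size (randomization is 1:1:1).

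Let C be subjects with protocol core MACE and D the other deaths.

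Ratio = (C_OCA + D_OCA) / (C_placebo + D_placebo)

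With equal other deaths in each arm:
- 20 v 30 alone: 30/20 = 1.50
- plus 8 per arm: 38/28 = 1.36
- plus 15 per arm: 45/35 = 1.29
- 20 v 24 alone: 24/20 = 1.20
- plus 8 per arm: 32/28 = 1.14
- plus 15 per arm: 39/35 = 1.11

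With unequal other deaths:
- 20 v 30, plus 15 on placebo and 10 on OCA: 40/35 = 1.14 (from 1.50)
- 20 v 24, plus 10 on placebo and 15 on OCA: 39/30 = 1.30 (from 1.20)

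**Step 4: the general rule.** The combined ratio is a weighted average:

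R = (1 − s) × R_CV + s × R_other, with s = D_placebo / (C_placebo + D_placebo)

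Check: s = 8/28 = 0.286 gives 0.714 × 1.50 + 0.286 × 1.00 = 1.36, as above.

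With R_other = 1 and s of 10%, 20%, 30% and 40%:
- R_CV = 1.5 becomes 1.45, 1.40, 1.35 and 1.30
- R_CV = 1.3 becomes 1.27, 1.24, 1.21 and 1.18
- R_CV = 2.0 becomes 1.90, 1.80, 1.70 and 1.60

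The result always moves towards the ratio for other deaths. That is towards 1 only if those deaths are balanced. For the three-component time-to-event endpoint s = 0, so nothing changes.

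**Step 5: the missing endpoint.** Taking unstable angina out of the protocol's four-component endpoint leaves exactly the protocol's core MACE. The composite has fewer events but gains no unrelated ones.

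**The case against.** The strongest defence is that the definition only describes what is sent for adjudication. The sentence does end with the charter, and all deaths do go to the committee. The summaries are of adjudicated cardiovascular events, and Protocol Appendix E separates non-cardiovascular deaths, including hepatobiliary, infectious and malignant causes. The charter is not among the documents. So it is not certain that other deaths would enter the tables. But the SAP words its parenthesis as a definition, offers no other, and in the next paragraph orders summaries of MACE by name. The literal reading is available to a programmer, and it is the wrong one.

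A reader might infer that the SAP dilutes its main cardiovascular time-to-event comparison. It does not, because that endpoint names cardiovascular death. A reader might also treat the loss of unstable angina as dilution. It is a departure from the protocol, but it narrows the composite and unstable angina is still analysed separately.

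Nor does SAP Section 11 prove an undisclosed change. SAP Section 1 says that Section 11 summarizes key changes from SAP V1.0, not every departure from the protocol, and V1.0 is not available. What stands is that nothing in this SAP explains the difference.

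Finally, it would be too much to say that a signal would be hidden. Cardiovascular death, infarction and stroke each have their own endpoint. The direction is not fixed either: Protocol Section 5.5 reports more serious hepatic events with OCA 25 mg than with OCA 10 mg or placebo, so other deaths need not be balanced. SAP Section 10.4.9.1 names no test, and Section 10 excludes inferential safety comparisons unless specified, so no loss of power is claimed.

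**Conclusion.** The MACE definition is wrong as written. It conflicts with the protocol's core MACE and with the first time-to-event endpoint in its own section. The exposure is limited to the MACE incidence and annualized-rate summaries, and depends on their being programmed from that definition. In that case the between-arm comparison would be distorted, towards 1 if other deaths are balanced and in either direction if they are not. The illustrated shift from 1.50 to 1.36 or 1.29 rests on assumed counts with equal other deaths per arm and is not an estimate for this trial.

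The absence of the four-component endpoint is a separate, unexplained departure from the protocol. It loses a planned composite but does not dilute the one that remains.

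**What to change.** In SAP Section 10.4.9.1:
- Define MACE as cardiovascular death (with undetermined causes counted as cardiovascular), nonfatal MI and nonfatal stroke, in line with Protocol Section 16.9.3.
- State that this definition drives all MACE incidence, rate and time-to-event tables.
- Keep death from any cause as its own endpoint.
- Restore the protocol's four-component first-event endpoint beside the three-component one.

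The cost is a change of SAP wording and one additional table. It should be made before the End of Study data are unblinded.

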Placebo and the 2 dose levels of OCA will be compared separately using a log rank test stratified by the randomization stratification factor. KM estimates of the distribution of the time-to-event will be tabulated and graphed by treatment group. Subjects without any documentation of events will be censored at the date of last contact. The tabulation will include the KM estimate of the medians and corresponding 95% CIs, if the medians can be estimated. The number and percent of subjects censored and with events will be presented. The hazard ratio and 95% CI will be determined based on a Cox regression model stratified by randomization strata to estimate the magnitude of the effect.

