#### **2.1.2.4. Safety Objectives Assessed at End of Study**

- To evaluate the effect of OCA compared to placebo on:
  - Incidence, exposure adjusted incidence rate and time to treatment-emergent pruritus
  - Incidence, exposure adjusted incidence and time to adjudicated cardiovascular events
  - Incidence and exposure adjusted incidence adjudicated acute kidney injury (AKI)

- Incidence, exposure adjusted incidence and time to adjudicated events of hepatic injury
- Long-term safety and tolerability (TEAEs, AESIs, ECGs, vital signs, clinical laboratory assessments)

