Time-to-event data will be summarized using Kaplan-Meier (KM) methodology using 25th, 50th (median), and 75th percentiles with associated 2-sided 95% CIs, as well as the percentage of censored observations. KM estimates will be plotted as a “survival curve” for each treatment group, with the number at risk identified. In addition, time-to-event data will be summarized with descriptive statistics for those subjects with an event. Subjects who do not experience an event will be censored. Subjects who do not experience an event will be censored at the date of last contact for clinical outcome endpoints and will be censored at the earliest date of last dose date+30 days, end of study, death date or date cut-off date for treatment-emergent adverse events (TEAEs). The censor date for time to resolution events will be the earliest date of end of study, death date or date cut-off date.

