## 10. SAFETY ANALYSES

Safety analyses will be conducted using the Safety Population including by treatment groups and total OCA (both OCA 25 mg and OCA 10 mg combined). If a subject is randomized to placebo and subsequently receives OCA, each TEAE (Section 10.3) will be attributed to the administered OCA dose.

No inferential comparison of safety endpoints will be performed, unless otherwise specified.

There will be 2 sets of safety summaries presenting the safety profile of the following populations:

1. The Safety Population as defined in Section 3.4
2. The ITT population as defined in Section 3.4

Frequencies of adverse events will be split into 2 periods: pre-Covid 19 (occurring on or before 30 Jan 2020) and post-Covid 19 (occurring after 30 Jan 2020). The data for both periods will be presented side-by-side by treatment group for the safety population.

Selected safety summaries will be prepared including all subjects in the mITT Efficacy Population. Summaries and listings will be presented by actual treatment received.

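### SAP 10.4.9.1 lists the time-to-first adjudicated cardiovascular endpoints but omits the stratified log-rank test and Cox hazard ratio that Protocol 16.9.3 requires, and Section 11 does not declare the change

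*SAP*

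**What the plan says.** Protocol 16.9.3 lists the adjudicated cardiovascular time-to-event endpoints and then gives a full method. On the test: "Placebo and the 2 dose levels of OCA will be compared separately using a log rank test stratified by the randomization stratification factor". On the estimate: "The hazard ratio and 95% CI will be determined based on a Cox regression model stratified by randomization strata". On censoring: "Subjects without any documentation of events will be censored at the date of last contact". It rules out formal testing of MACE only at the Month 18 Interim Analysis, and adds: "The EOS assessment of MACE will include all MACE events occurred from the start of the study".

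The SAP keeps the objective. Section 2.1.2.4, on the effect of OCA compared with placebo, names "Incidence, exposure adjusted incidence and time to adjudicated cardiovascular events". Section 10.4.9.1 promises an "annualized adjudicated CV event rate, and a time-to-event analysis as described below". Below that sentence come eleven endpoint definitions, lipid summaries, risk subgroups and two lines on exposure-adjusted incidence rates (EAIR).

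Two SAP defaults apply where a subsection is silent. Section 4: "Time-to-event data will be summarized using Kaplan-Meier (KM) methodology", meaning percentiles, confidence intervals and curves for each arm. Section 10: "No inferential comparison of safety endpoints will be performed, unless otherwise specified".

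**The concern.** The promise in 10.4.9.1 points to a description that is not there, and the defaults that fill the gap lead away from the protocol. A programmer working from the SAP would produce curves and rates by arm, but no log-rank test and no hazard ratio for adjudicated MACE. With the two documents in conflict, the choice to run the comparison could be left until treatment assignments are known.

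The objective is not a minor one. Protocol 5.5 reports that OCA raises LDL cholesterol, says no conclusion about cardiovascular effect can yet be drawn, and says longer treatment and larger numbers are needed. This trial is projected to run about 10 years, and subjects who stop investigational product are expected to stay in follow-up. A comparison from randomisation to last contact uses that follow-up. One tied to time on drug does not use it fully.

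**Working it through.** The plan states no MACE count, rate, margin or power, so there is no figure to reproduce. The main check is textual.

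**Step 1. The two documents side by side, for adjudicated cardiovascular endpoints**

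| Element | Protocol 16.9.3 | SAP 10.4.9.1 |
|---|---|---|
| Test | Stratified log-rank, each dose vs placebo | None stated |
| Effect estimate | Stratified Cox HR, 95% CI | None stated |
| Censoring | Last contact | None stated |
| First composite | CV death, nonfatal MI, nonfatal stroke, or nonfatal unstable angina requiring hospitalization | CV death, nonfatal MI, nonfatal stroke |

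**Step 2. Do SAP defaults fill the gaps?**
- Section 4 supplies Kaplan-Meier summaries only, with no log-rank test or hazard ratio.
- Section 4 censors clinical outcome endpoints at last contact, and treatment-emergent adverse events no later than 30 days after last dose. Adjudicated cardiovascular endpoints are assigned to neither rule.
- Section 10 excludes inferential comparison unless specified. Nothing in 10.4.9.1 specifies one.
- Section 6.4.4.2 writes out the stratified log-rank test and Cox model, but for the primary clinical outcomes composite.
- Section 11 records additions for adjudicated cardiovascular data and no removal.

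**Step 3. What remains**
- Crude incidence with exact binomial 95% CIs, Kaplan-Meier by arm, and an annualized adjudicated event rate.
- Section 10.4 plans an EAIR difference with 95% CI from a Poisson model with treatment as the only explanatory variable. Cardiovascular is a listed event of special interest, but those categories are built from MedDRA queries. For a subject without an event, person-time ends at the earliest of last dose plus 30 days, study discontinuation, death or data cut-off.
- Section 10.4.9.1 adds EAIR by arm for adjudicated cardiovascular cases, without saying that a difference will be calculated.

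**Step 4. Illustration with assumed counts**

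Assume equal person-time in one OCA arm (d1 events) and placebo (d0 events), so HR ≈ d1/d0.
- HR limits: exp[ln(d1/d0) ± 1.96 × √(1/d1 + 1/d0)].
- Rate-difference limits, in events per arm's person-time: (d1 − d0) ± 1.96 × √(d1 + d0).

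| d0 vs d1 | HR | 95% CI for HR | Rate difference, 95% CI |
|---|---|---|---|
| 20 vs 30 | 1.50 | 0.85 to 2.64 (SE 0.289) | 10, −3.9 to 23.9 (SE 7.07) |
| 40 vs 59 | 1.48 | 0.99 to 2.20 | not calculated |
| 40 vs 60 | 1.50 | 1.01 to 2.24 (SE 0.204) | 20, 0.4 to 39.6 (SE 10) |

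Precision at an observed HR of 1.0, with D events in the two arms together and SE = 2/√D:
- D = 30: 0.49 to 2.05
- D = 60: 0.60 to 1.66
- D = 100: 0.68 to 1.48
- D = 150: 0.73 to 1.38

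This is the kind of statement that the protocol analysis would give and the SAP as written would not. With equal person-time, the rate difference and the hazard ratio agree on whether the null is excluded. They can part when time on drug differs between arms or when events occur after stopping. These counts do not illustrate that.

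**The case against.** The strongest reply is that the SAP is not empty. A reader might infer that only separate binomial intervals by arm remain, or that the trial could state no upper limit on MACE risk. Neither inference is supported. The Section 10.4 rate difference has a confidence interval, hence an upper limit, and it uses person-time, so it does not ignore unequal follow-up. Kaplan-Meier curves also handle unequal follow-up. The overall summary of events of special interest is run both on treatment and during study, and the annualized rate in 10.4.9.1 carries no stated last-dose limit. In the 40 versus 60 example the rate difference also excludes zero. All of this stands.

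It does not close the gap. The rate difference is written for MedDRA-query categories, is unstratified, and truncates follow-up of event-free subjects relative to the protocol. Whether it applies to adjudicated MACE is not stated.

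A second reply is that the SAP does not revoke the protocol, and that the protocol itself could count as having specified the comparison. The first half is right: the documents show an omission, not a decision to remove the analysis. The second half is a possible reading, but the SAP is where Protocol Section 16 says the specific planned analyses and tests are detailed, and nothing in it sends the reader back to Protocol 16.9.3 for this method.

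A third point is that subsection 10.4.9.3 does not appear in the public copy, so not all of the cardiovascular section can be checked. That is a fair limit, although 10.4.9.1 is visible and contains the unfulfilled pointer.

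**Conclusion.** The concern holds as a mismatch between protocol and SAP on a named safety objective. As written, the SAP yields no hazard ratio and no log-rank comparison for adjudicated MACE, assigns no censoring rule to these endpoints, and does not declare the departure in Section 11. The contrasts that remain are useful, but they do not replace a stratified comparison of adjudicated events from randomisation to last contact.

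Its size cannot be taken from the documents. The counts in the working are assumed, and the result moves with them: one event fewer than 60 takes the interval across 1, and 20 versus 30 events at the same hazard ratio gives 0.85 to 2.64. They are scenarios, not a forecast. The textual finding does not depend on them. It rests on the visible SAP text and on reading Section 10's exclusion as applying where 10.4.9.1 is silent.

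This should be corrected before the end-of-study database lock. It affects a safety objective and leaves the primary endpoint untouched.

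**What to change.** Amend SAP 10.4.9.1 to state:
- For each listed time-to-event endpoint, each OCA dose is compared with placebo by hazard ratio and two-sided 95% CI from a Cox model stratified by the randomisation strata, with the stratified log-rank test.
- Adjudicated events count from randomisation, and subjects without an event are censored at last contact.
- P-values are nominal. There are 11 endpoints and 2 doses, so 22 tests, with no multiplicity control.
- The population is named. The section now uses both Safety and ITT, and the main one should be stated. If stage 1 subjects are included, say how they enter the strata, because the protocol describes stratification for stages 2 and 3.
- This is an exception to the no-inference sentence in Section 10.

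Reconcile the first composite: the protocol includes unstable angina requiring hospitalization and the SAP does not. Also align the MACE definition, where the SAP text has death and the protocol has cardiovascular death. Say whether the Section 10.4 rate difference applies to adjudicated cardiovascular events.

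If the sponsor does intend to omit the comparison, declare and justify that in Section 11.

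The cost is SAP wording and a few tables. No new data are needed.
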